PROVESA trial

Proficiency based progression training for robotic vesico-urethral anastomosis chicken model versus the Halsted's model: a cross-specialty, multicentric, randomized and blinded clinical trial.

Study Protocol

Principal Investigator: [name] [name]

Research center: ORSI Academy, Melle, Belgium

July 27th 2020

NCT ID not yet assigned

Ethical Committee approval number 22072020

Summary

In a prospective, randomized and blinded study robotic naïve (urology ($n = 12$), surgery ($n = 12$) and gynecology ($n = 12$)) residents ($n = 36$) from the KU Leuven and University of Gent residency training programs will be randomized (in equal discipline numbers) to Traditional Halstedian apprenticeship type training or proficiency based progression (PBP) training to learn to perform a vesico-urethral anastomosis (VUA) on a chicken model. Both groups will receive the same e-learning (on how to perform the VUA on the chicken model) and skills laboratory robotic training curriculum. The PBP trained group will however be required to demonstrate quantitatively defined proficiency benchmarks for training progression (i.e., from e-learning to the skills lab). The PBP group will also have a defined benchmark to demonstrate before training is deemed completed. The Traditional trained group will train in the same skills laboratory for a case-matched period of time as the PBP group, with the same level of supervising faculty proctors and using the same training resources but with no proficiency benchmarks or metric-based feedback. Both groups will be required to perform a VUA on the chicken model before skills training proper and at the end of training. Investigators will be trained in pairs to assess VUA performance from a pre-defined set of explicitly defined binary metric events reliably (inter-rater reliability > 0.8). They will also be blinded as to the identity of the trainee performing the procedure, how they were trained (i.e., group) and procedure order.

H₁ It is hypothesised that implementation of PBP training in teaching the robotic suturing of VUA leads to better surgical training outcomes (i.e., lower number of performance errors) when compared to Halsted's method.

Proficiency based progression training for robotic vesico-urethral anastomosis chicken model versus the Halsted's model: a prospective, randomized and blinded clinical trial.

Introduction

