Fundamental in creating a proficient robotic surgeon is the acquisition of basic surgical skills, such as suturing and knot tying.¹³ Some training models mimic the real anatomical environment in which a procedure will be performed and provide trainees with the opportunity to learn and practice their skills before starting their practice on real cases in the operating room. Numerous dry-lab, wet-lab, and virtual reality simulation models have been described.¹⁴ The "Venezuelan chicken model" is generally accepted as a optimal model for trainees to learn robotic suturing, anastomosis and knot tying tasks (for all surgical disciplines).¹⁴⁻¹⁶ We will use the Venezuelan chicken model in this study. It has several advantages; it is inexpensive, widely available, easy to prepare, it is a good model for the urethro-vesical anastomosis training, it is possible to introduce a catheter and performing the leakage test, it takes the trainee approx. 20 mins to complete the task. Over the past 12 months ORSI has developed and validated (Delphi consensus and Construct Validity) performance metrics for the task.

This study aims to compare the effectiveness of Halsted's apprenticeship approach to training with the Proficiency Based Progression (PBP) approach for teaching the robotic suturing of a vesico-urethral anastomosis (VUA) on a chicken model.

Methods

Subjects

Robotic naïve urology ($n = 12$), surgery ($n = 12$) and gynecology ($n = 12$) residents ($n = 36$) from the UKU Leuven and University of Gent residency training programs will participate. They will be randomized (using an online randomizer <https://www.random.org/>) to teaching of VUA suturing with either Halsted's ($n = 18$) or the PBP method including procedure-specific, validated metrics ($n = 18$).

Procedure and training

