Investigators will be trained in pairs to assess performance from a pre-defined set of explicitly defined metric events reliably (inter-rater reliability > 0.8). They will be blinded as to the identity of the trainee performing the procedure, how they were trained (i.e., group) and procedure order.

Procedure performance assessment

[figure not shown]
We will record how long subjects took to perform the procedure, the number of steps correctly completed and procedure errors/deviations from optimal performance. We will also record and cost the instrumentation/needles/suture etc utilised in the performance of the procedure.

Baseline Assessment: -Prior to the commencement of education and training protocol all subjects from both groups will be assessed on their performance of the VUA task. Performance on the procedure will be video recorded and assessed as previously described.

Statistical Analysis: From previous similar studies, it has been found that data has been reasonably normally distributed and suitable for parametric statistical analysis. If the data violates any of the assumptions of normality, data will be compared for statistical significance with Mann-Whitney U for comparison between two independent samples and Wilcoxon signed-rank test. Where data are normally distributed with approximately equal variance differences between groups, task performance will be compared for statistical significance with two-factor Analysis of Variance where factor one is the type of training subjects received and factor two is the order the task was performed (i.e, baseline

performance and end of training performance). The same analysis will be used to assess the binary checklist metric scores and the GEARS scores (seperately) for the Standard trained and the PBP trained groups. Specific post hoc statistical contrasts between surgeon groups performance within a training condition (i.e., between the objectively assessed performance of urology, surgery and gynecology residents) will be done with Scheffe F-tests.

Statistical power calculation: A pilot study has shown that novices on average make 16.6 (SD = 4) performance errors on the task. Assuming a reduction of ~40% with PBP training (i.e., 16.6 vs 10 errors) with a standard deviation of n = 4, an Alpha – 1% with 16 subjects in each group would yield a statistical power of 0.998 for the proposed study.

* By assessors blinded to group membership and procedure order (first or last procedure)

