** Matching according to specialty

Figure 1. the design of the prospective randomized study to evaluate the impact of PBP on learning the robotic surgical skills for a vesico-urethral anastomis (VUA) on a chicken model.

Hypothesis

- H₁ Implementation of PBP training in teaching the robotic suturing of VUA leads to better surgical training outcomes (i.e., lower number of performance errors) when compared to Halsted's method.
- H₀ There will be no difference in the procedure knowledge prior to VUA training
- H₀ There will be no difference in the objectively assessed procedure performance of the urology, surgery and gynecology residents at the end of training in the PBP group
- H₀ There will be a difference in the objectively assessed procedure performance of the urology, surgery and gynecology residents at the end of training in the Traditional trained groups.
- H₀ There will be no difference in student satisfaction with the two approaches to training.

Depth perception				
1	2	3	4	5
Constantly overshoots target, wide swings, slow to correct		Some overshooting or missing of target, but quick to correct		Accurately directs instruments in the correct plane to target
Bimanual dexterity				
1	2	3	4	5
Uses only one hand, ignores nondominant hand, poor coordination		Uses both hands, but does not optimize interaction between hands		Expertly uses both hands in a complementary way to provide best exposure
Efficiency				
1	2	3	4	5
Inefficient efforts; many uncertain movements; constantly changing focus or persisting without progress		Slow, but planned movements are reasonably organized		Confident, efficient and safe conduct, maintains focus on task, fluid progression
Force sensitivity				
1	2	3	4	5
Rough moves, tears tissue, injures nearby structures, poor control, frequent suture breakage		Handles tissues reasonably well, minor trauma to adjacent tissue, rare suture breakage		Applies appropriate tension, negligible injury to adjacent structures, no suture breakage
Autonomy				
1	2	3	4	5
Unable to complete entire task, even with verbal guidance		Able to complete task safely with moderate guidance		Able to complete task independently without prompting
Robotic control				
1	2	3	4	5

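### The paired specialty hypotheses (no difference in PBP, a difference in Traditional) are examined only by within-arm Scheffe contrasts on 6 residents per cell, which can show neither equality in PBP nor a training-dependent specialty gap

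*Combined protocol and SAP*

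**What the plan says.** The Hypothesis section lists H1 (fewer errors with PBP) and four further statements, all labelled H₀. Two of these concern specialty. For the PBP arm: "There will be no difference in the objectively assessed procedure performance of the urology, surgery and gynecology residents at the end of training". For the Traditional arm: "There will be a difference in the objectively assessed procedure performance of the urology, surgery and gynecology residents at the end of training".

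The Statistical Analysis paragraph gives a two-factor ANOVA in which "factor one is the type of training subjects received and factor two is the order the task was performed". Specialty is not a factor in it. Specialty is handled separately: "Specific post hoc statistical contrasts between surgeon groups performance within a training condition", by Scheffe F-tests. No alpha, error term, equivalence margin or confidence-interval criterion is given for these contrasts.

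By the Summary, residents "will be randomized (in equal discipline numbers) to Traditional Halstedian apprenticeship type training" or to PBP. With 12 residents per specialty and 18 per arm (Subjects section), each specialty has 6 residents in each arm.

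**The concern.** A predicted difference is an alternative hypothesis, so the H₀ label on the Traditional line is wrong. The PBP line is a valid null. Relabelling changes nothing in the analysis, because a Scheffe test has equality as its null whatever the heading says.

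What matters is the pairing. The two statements are set out in advance beside H1, and together they suggest that specialty matters under one form of training and not under the other. The planned contrasts cannot carry that message, for two reasons:

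- With 6 per group, a non-significant result in PBP is likely even if the specialties differ appreciably, so it does not show that they perform alike.
- One significant and one non-significant result do not show that the two arms differ from each other. That requires a direct comparison of the specialty gaps between arms, and none is planned.

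At stake is a report that PBP levels out specialty differences when the gap may be the same in both arms.

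**Working it through.** **The plan's own figure.** The only power figure (0.998; 16.6 versus 10 errors, SD 4, alpha 1%, 16 per arm) concerns the two-arm comparison. A two-sided normal approximation gives 0.982, which is close enough that nothing here turns on it. There is no figure for the specialty questions to reproduce.

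**Inputs from the documents.** Cell size is 36/(3 × 2) = 6. The Statistical power calculation paragraph says "novices on average make 16.6 (SD = 4) performance errors on the task", so SD 4 is the base case.

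**Assumptions.** Alpha is 5%, with 1% also shown, because none is stated for these contrasts. SD 3 and 2 are shown because no end-of-training SD is given. The specialty gaps are chosen, since the documents give none. The error term is within-arm, 15 df.

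**1. Smallest significant pairwise gap.** The critical value is √(2 × F(0.95; 2, 15)) = 2.714. The standard error is SD × √(2/6), which is 2.309 at SD 4. The gap is 2.714 × 2.309 = 6.27 errors. Pooling the error over both arms (30 df) gives 5.95. Power is from the noncentral t.

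| SD | Gap needed, alpha 5% | Gap needed, alpha 1% | Power for a 4-error gap, alpha 5% |
|---|---|---|---|
| 4 | 6.27 | 8.24 | 20% |
| 3 | 4.70 | 6.18 | 37% |
| 2 | 3.13 | 4.12 | 76% |

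At SD 4 and alpha 1%, power for a 4-error gap is 7%. For scale, the whole training effect assumed in the plan is 16.6 − 10 = 6.6 errors.

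**2. Can the PBP data show equality?** Suppose two specialties are truly equal and equivalence means that the 90% CI lies inside a margin. A 4-error margin is met 10%, 43% and 90% of the time at SD 4, 3 and 2. All three pairs meet it together 3%, 20% and 79% of the time (400,000 simulated trials).

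**3. How often does Traditional-only significance arise with no training-dependent gap?** Give both arms specialty means (−d/2, 0, d/2). If p is the chance that at least one pair is significant in an arm, the chance of the pattern is p(Traditional) × (1 − p(PBP)). By simulation at SD 4 and alpha 5%, p is 0.236 for d = 4 and 0.503 for d = 6.

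| SD Traditional / PBP | Alpha | d = 4 | d = 6 |
|---|---|---|---|
| 4 / 4 | 5% | 0.236 × 0.764 = 18% | 0.503 × 0.497 = 25% |
| 3 / 3 | 5% | 24% | 17% |
| 2 / 2 | 5% | 17% | 1% |
| 4 / 3 | 5% | 14% | 11% |
| 4 / 2 | 5% | 5% | 1% |
| 4 / 4 | 1% | 7% | 18% |

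Under the same equal spread (d = 4), a training-by-specialty F test at 5% is falsely positive 5.1% of the time at SD 4 in both arms, and 5.6% at SD 4 and 2.

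**4. What the interaction test can detect.** Take means (−2, 0, 2) in Traditional and equal means in PBP. Each extreme cell in each arm then has an interaction effect of ±1, so λ = 6 × 4 × 1²/SD² = 24/SD². The noncentral F(2, 30) gives power of 17%, 27% and 54% at SD 4, 3 and 2. The 95% CI half-width for one between-arm difference of specialty differences is t(0.975; 30) × SD × √(4/6) = 6.7, 5.0 and 3.3 errors.

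**The case against.** The strongest reply is that the harm is hypothetical. The plan never says that a non-significant PBP result will be taken as equality, and never says that the arms' verdicts will be compared. It calls the contrasts post hoc, and the Summary states only H1. All of this is right, and it limits the point to what the paired hypotheses invite.

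Three stronger readings are tempting, and the documents support none of them:

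- A reader might infer that the H₀ label makes the Traditional test wrong. It does not; the test is the same under either label.
- A reader might infer that the plan claims a training-dependent specialty gap. No sentence says so.
- A reader might infer that the Traditional prediction cannot be supported at all. A significant contrast there would be valid evidence within that arm, though power is low.

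The size of the chance pattern also depends on inputs that the documents do not supply. PBP trainees must reach a benchmark before training is deemed complete, so a smaller spread or SD in that arm is plausible. With a smaller PBP SD the rates fall, as the table shows. At alpha 1%, the only alpha in the document, the SD 4 rates fall as well.

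Finally, an interaction test with 17% power at SD 4 will usually be non-significant even if the predicted pattern is true. That stands. It argues for intervals and careful wording rather than for leaving the between-arm question without a valid analysis.

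**Conclusion.** The concern holds in this limited form: the planned within-arm contrasts cannot establish no difference among specialties in PBP, and cannot establish that training changes the specialty gap. The paired hypotheses invite both conclusions without stating either.

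In the base case (SD 4, alpha 5%), only observed gaps above about 6.3 errors are significant, and a true 4-error gap is missed four times in five. With equal spread in both arms, the Traditional-only pattern arises by chance about 18% to 25% of the time. That range is 7% to 18% at alpha 1%, 11% to 14% if the PBP SD is 3, and about 5% or less if it is 2. These rates rest on assumed gaps of 4 to 6 errors between the extreme specialties, and on the pilot novices' SD applying at end of training in the Traditional arm.

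Only secondary hypotheses are touched and H1 is unaffected, so the priority is low to moderate.

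**What to change.** 1. Reword the Traditional null as no difference among specialties, with the expected difference as its alternative.
2. For errors, and likewise for the other performance scores that the Statistical Analysis paragraph covers, fit an end-of-training model with training, specialty and training by specialty (2-df interaction test). Limiting this to errors would be narrower than the hypotheses, which refer to objectively assessed performance in general.
3. If specialty is instead added to the repeated-measures ANOVA, use the end-of-training training-by-specialty contrast, or the three-way term for change from baseline. The term averaged over baseline and end of training does not answer the stated hypotheses.
4. Report specialty differences in each arm, and their between-arm differences, with 95% CIs, labelled exploratory.
5. State that non-significance will not be read as equality (such a claim would need a margin set in advance), and that the arms will not be compared by their separate significance verdicts.
6. The Scheffe contrasts can stay as follow-up. State their alpha and error term. The non-parametric fallback names only Mann-Whitney and Wilcoxon signed-rank tests, so also say how three specialties would be compared if normality fails.

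The cost is rewording, one small model per score and two sentences on interpretation; no extra data are needed. The drawback is that the interaction test is weak. The gain is correct interpretation, not power.
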